8.7.3. Summaries of Adverse Event Incidence Rates for All Patients

The number and percentage of patients who experienced TEAEs will be presented by SOC and by PT within SOC for each treatment group. Treatment-emergent AEs (TEAEs) will be similarly presented by severity (mild, moderate, severe), by relationship to study drug (unrelated, definite, probable, and possible) and by outcome of events. Additionally, the number of TEAEs (as opposed to the number and percentage of patients) will be presented by treatment group.

The number of patients with TEAEs and number of TEAEs will also be presented by the following subgroups of Age (28 days to <2 years, 2 years to <12 years, 12 years to ≤18 years, >18 years). Subgroups for age are defined based at the patient's age at Baseline.

To count the number of patients who experienced each TEAE, a patient experiencing the same TEAE multiple times will only be counted once for the corresponding PT. Similarly, if a patient experiences multiple TEAEs within the same SOC, the patient will be counted only once for that SOC. If a patient experiencing more than one TEAE within different severity or relationship categories within the same SOC/PT, only the worst case (worst severity and related TEAE) will be reported. TEAEs will be sorted alphabetically by SOC and within each SOC the PT will be presented by decreasing order of total frequency.

For TEAE summary by outcome, if a patient experienced more than one TEAE, the worst outcome will be counted under that patient. If a patient experienced more than one outcome within a SOC (or PT), the patient is only counted once under worst outcome in that SOC (or PT).

In addition, all adverse events will be provided by study site and by treatment group, in a listing, which will include the patient identifier, the PT, the reported term, the severity, the seriousness, the action taken, the outcome, the causality, the date onset, date of onset relative to the date of the first study drug administration, date of resolution, date of resolution related to the first study drug administration, and the TEAE duration (resolution date –onset date +1).

Additionally, the incidence and the number of non-serious TEAEs will be presented by treatment group.

Non treatment-emergent AEs, if any, will be listed.

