7. STATISTICAL METHODS

7.1. General Methodology

The final analysis after the study completion will be preceded by at least one interim analysis.

Data will be summarized by treatment groups (based on 005 study treatment: Placebo → SD-101-6.0 and SD-101-6.0 → SD-101-6.0) and overall (where appropriate). Summary and analysis tables will include number of patients (n), mean, standard deviation, median, minimum, and maximum values for all continuous variables. When appropriate, two-sided 95% confidence intervals may be used.

In summary tables of categorical variables counts and percentages will be presented. The denominator for each percentage will be the number of patients within the population (unless otherwise specified).

All analyses for efficacy will be performed using the Intent-To-Treat (ITT) population, all safety analyses will be performed using the safety population. No comparison between treatment groups will be performed. The comparison to baseline will be done by visit in Placebo → SD-101-6.0 group. All hypothesis testing will be two-sided. P-values less than 0.001 will be reported as <0.001 in summary tables.

All statistical analysis will be performed using SAS[®] v9.2 or higher.

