8.7. Analysis of Safety

8.7.1. Extent of Exposure

No diary data were collected on whether a patient used or did not use SD-101-6.0 on a given day. Therefore the number of days on the study will be considered number of days of exposure. It will be summarized using descriptive statistics by overall. Descriptive statistics will also be provided for duration of exposure into categorical summary of <30, >=30 to <90, >=90 to <180, >=180 to <1 year, >=1 year to <2 years, >=2 years.

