8.7.4.3. Missing Relationship

If the assessment of relationship of the AE to study treatment is missing for any AE, then it will be presented as missing in the listings and in the summary tables.

8.7.5. Summaries of Adverse Incidence Rates for Serious Adverse Events (SAE), Adverse Event Dropouts, and Death

During the treatment period, the number and percentage of patients who experienced TESAEs and separately TEAEs leading to withdrawal from the study will be presented by SOC and by PT within each SOC for each treatment. Treatment-emergent SAEs and separately TEAEs resulting in withdrawal from the study will be similarly presented by severity (mild, moderate, severe), by relationship to study drug (related would include definite, probable, and possible) and by outcome of events. Additionally the number of TESAEs (as opposed to the number and percentage of patients) and separately TEAEs leading to withdrawal will be presented.

Number of patients with TESAEs and separately TEAEs resulting in withdrawal as well as number of TESAEs and separately the number of TEAEs leading to withdrawal will also be presented by the following subgroups of Age (28 days to <2 years, 2 years to <12 years, 12 years to <=18 years, >18 years), EB type and independently. Subgroups for age are defined based at the patient's age at Baseline.

In case that there are non-treatment emergent serious adverse events, they will be listed.

A listing of all serious adverse events and discontinuations due to AEs will be included. Patient with deaths, SAEs or patients who withdraw due to AE will be listed separately and discussed with patient narratives.

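### Long-term safety is the primary objective, but the planned adverse event tables give only crude patient percentages and event counts, with no person-time rate and no summary by time on treatment

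*SAP*

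**What the plan says.** Long-term safety is the primary objective (Protocol 7.1, SAP 3) and the primary endpoint (Protocol 9.2).

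- **All TEAEs (SAP 8.7.3).** "The number and percentage of patients who experienced TEAEs will be presented by SOC and by PT within SOC for each treatment group". The same layout is repeated by severity, relationship, outcome and age group, with counts of events added.
- **Serious TEAEs and TEAEs leading to withdrawal (SAP 8.7.5).** Here "the number and percentage of patients who experienced TESAEs and separately TEAEs leading to withdrawal from the study will be presented by SOC", again with counts.
- **Denominator (SAP 7.1).** "The denominator for each percentage will be the number of patients within the population", unless another is specified. The adverse event sections specify none.
- **Timing.** The adverse event listing in SAP 8.7.3 includes "date of onset relative to the date of the first study drug administration". No summary table uses it.
- **Exposure (SAP 8.7.1).** No diary was kept, and time on study stands in for use: "Therefore the number of days on the study will be considered number of days of exposure". The grouping for this summary differs from the general rule below: "It will be summarized using descriptive statistics by overall". Six duration bands are planned as well, from under 30 days to 2 years or more. The bands are not crossed with adverse events.
- **Grouping (SAP 7.1).** "Data will be summarized by treatment groups", meaning the two SD-005 arms, and overall where appropriate.

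Protocol 14.3 and the titles of SAP 8.7.3 and 8.7.5 speak of incidence rates, without defining a time denominator.

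**The concern.** A long-term safety study should say how often adverse events occur for a given amount of use, and whether the risk rises, falls or stays level as use continues. A crude percentage answers neither question when patients are followed for different lengths of time, because it mixes risk with duration of follow-up.

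Unequal follow-up is likely here. Patients enter as they finish SD-005, some may drop out, and a single letter of 4 June 2018 stopped application at all sites (SAP 5.1). SAP 6.4.1 accepts that data at later time points will be limited. SAP 7.1 also plans at least one interim analysis before the final one, so a crude percentage can grow between data cuts simply because patients have been followed longer.

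The adverse event tables carry this question almost alone. Physical examination and vital signs are scheduled only at baseline and the final visit. Apart from pregnancy tests, adverse events are the only safety outcome that the SAP analyses and that is collected at repeated visits. The secondary efficacy measure, BSAI, does get summaries by visit and graphs over time (SAP 8.6.1).

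**Working it through.** The plan states no adverse event rate, precision target or expected follow-up distribution, so there is no figure to reproduce. The event rates below are assumptions. The times 180 days, 1 year and 2 years are cut points in SAP 8.7.1.

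**1. Effect of follow-up length at constant risk.** Crude percentage = 1 − exp(−r × t), with r in first events per patient-year and t in years (180 days = 180/365.25 = 0.493).

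| Assumed r | 180 days | 1 year | 2 years |
|---|---|---|---|
| 0.02 | 1.0% | 2.0% | 3.9% |
| 0.2 | 9.4% | 18.1% | 33.0% |
| 0.5 | 21.8% | 39.3% | 63.2% |

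Underlying risk is identical along each row. In absolute terms the spread is large for common events and small for rare ones.

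**2. Change of risk over time, with everyone followed for 2 years.** This is a separate point: follow-up is equal here, so only the trend is hidden. Fix the cumulative risk at H = 0.2 × 2 = 0.40.

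- Flat: 0.20 + 0.20 = 0.40
- Rising: 0.05 in year 1, then 0.40 − 0.05 = 0.35 in year 2 (seven-fold rise)
- Falling: 0.35 in year 1, then 0.05 in year 2 (seven-fold fall)

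In all three, patients with an event = 1 − exp(−0.40) = 33.0%. If the same rates also govern repeat events, expected events are 0.40 per patient, and 0.40/2 = 20 per 100 patient-years. The planned percentages and counts would be the same for all three.

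**3. Would one overall person-time rate be enough?** For the first-event rate, mean time at risk for rates a (year 1) and b (year 2) is (1 − e^−a)/a + e^−a × (1 − e^−b)/b.

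- Flat: 0.330/1.648 = 20.0 per 100 patient-years
- Rising: 0.330/1.778 = 18.5
- Falling: 0.330/1.531 = 21.5

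A seven-fold change in risk moves the overall first-event rate by only 1.5 per 100. A table by interval shows it directly: 5 against 35 per 100 patient-years in the two years.

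**4. Precision of interval rates (exact Poisson limits).** 20 events in 100 patient-years give 20 per 100 (95% CI 12.2 to 30.9). 5 events in 30 patient-years give 16.7 per 100 (5.4 to 38.9).

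**5. Which window?** SAP 6.2.1 defines a study day from consent and a relative day from first application. SAP 8.7.1 does not say which one its days on study use, nor when they end. For the event count, SAP 8.7.2 treats events before first application as not treatment-emergent, and SAP 6.5.2 collects events through the last study visit. The matching person-time therefore runs from first application to last study visit.

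**The case against.** **This is a descriptive, single-treatment study with no planned group comparison, so nothing is biased.** That stands, and it limits the weight of the point. A reader might infer that the safety results are invalid, or that the two prior-treatment groups are compared unfairly. The documents support neither: SAP 7.1 rules out between-group comparison, and nothing shows that follow-up differs between the groups.

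**The information is already in the report.** Partly true. An overall event rate can be worked out from the event count, the number of patients and mean exposure, and onset times are listed. But that gives one figure without a trend, and reworking a patient listing is not a planned summary.

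**The protocol promised rates and the SAP dropped them.** A reader might infer this from Protocol 14.3. The wording there has no time denominator and may be loose usage for percentages, so it is not a broken commitment.

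**The dates in SAP 5.1 give the actual size.** A reader might count from 2 December 2015 and 10 November 2016 to 4 June 2018, obtaining 915 and 571 days, and hence 39% against 27% at 0.2 per year. Those are the dates on which the amendments were finalised, not entry dates. A patient entering on 2 December 2015 would have reached day 360, the study length before amendment 2, on 26 November 2016. That is 16 days after the amendment was finalised, and whether such a patient could continue is unknown. Nor do the exposure bands in SAP 8.7.1 prove unequal follow-up; they are only table categories.

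**Interval tables can mislead too.** This stands and shapes the fix. Patients from the SD-101-6.0 arm of SD-005 had already used the product, so pooling them with new users blurs time on treatment. SAP 8.7.4.1 imputes missing parts of start dates early, which could create an apparent decline in risk.

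**Conclusion.** The point holds as a limit on descriptive interpretation. The planned tables neither allow for length of follow-up nor show how adverse event risk changes with longer use, although long-term safety is the primary objective. This is a worthwhile and inexpensive improvement, not a flaw that invalidates the analysis.

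The size cannot be established from the documents. The figures above rest on assumed rates, a constant rate in the first calculation, and rates constructed to match in the second. Whether actual follow-up was unequal, and by how much, is likely but not documented.

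Two smaller matters sit alongside. SAP 8.7.1 gives exposure overall only, while the general rule in SAP 7.1 is by group and overall where appropriate; this is probably a drafting slip, but should be reconciled. SAP 8.7.1 should also say which day definition from SAP 6.2.1 it uses and give an end date.

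**What to change.** 1. **SAP 8.7.1.** Define one at-risk window, from first application in SD-006 (the relative day in SAP 6.2.1) to last study visit, and use it for both events and person-time. Report days and total patient-years by prior-treatment group and overall. If dates allow, add a flagged summary ending at last application or at 4 June 2018.
2. **SAP 8.7.3 and 8.7.5.** For TEAEs, serious TEAEs and TEAEs leading to withdrawal, add two rates per 100 patient-years with 95% CIs: patients with a first event (time ends at that event) and all events (all time in the window).
3. **By interval.** Show these rates by time since first SD-006 application, for example 0–6, 6–12, 12–24 and over 24 months, with the number at risk. Present Placebo → SD-101-6.0 and SD-101-6.0 → SD-101-6.0 separately, noting the latter's earlier exposure in SD-005. Merge sparse intervals.
4. **Check on imputed dates.** Repeat the interval table without events whose start date was imputed under SAP 8.7.4.1.

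**Cost.** SAP wording and a few extra tables, with no new data collection. Late intervals will be imprecise, as the 5-event example shows. Time to last visit includes some days off treatment after the stop letter; each week adds 7/730.5 = 1.0% to a two-year window, which the flagged summary in step 1 addresses.

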8.7.4. Missing AE Onset, Severity, and Relationship

8.7.4.1. Missing or Partial AE Dates

The following list describes how partially missing date information will be handled as it relates to partial or missing start dates. Partial dates will be imputed as follows

1. If year is not missing and is after the year of first application of study drug:
 - a. If Month is missing, then Month will be imputed as January.
 - b. If Day is missing, then Day will be imputed as the first of the month.
3. If year is not missing and is the same as the year of the first application of study drug:
 - a. If Month is missing, then impute the Month as the month of the first application of study drug.
 - b. If Day is missing but Month is on or after the month of first application of study drug, then impute Day as the first day of the month.

- c. If the Day and Month are missing then impute Day and Month as the Day and Month of the first study drug application.
4. If year is missing, then impute the year as the year of the first study drug application:
 - a. If Month is missing, then impute the Month as the Month of the first study drug application.
 - b. If Day is missing, then impute the Day as the day of the first study drug application.
5. If the start date is completely missing, but the AE is either ongoing or the stop date is after the first date of drug application, then impute the start date as the first date of study drug application.
6. If using the above rules, the stop date is before the start date, then leave the stop date missing and assume that AE is treatment-emergent for the purpose of the analysis.

Completely missing stop dates will not be imputed. The partial stop dates will be imputed as follows:

1. If the year is missing, the stop date will not be imputed.
2. If the month is missing, then the month will be imputed as December.
7. If the day is missing, then the day will be imputed as the last day of the month.

Imputed dates will be flagged in the individual supportive patient listings.

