6.5.2. Adverse Events

Treatment-emergent adverse events (TEAEs) are any untoward medical occurrence in a patient, administered a medicinal product and which does not necessarily have to have a causal relationship with this treatment. An adverse event (AE) can therefore be any unfavorable and unintended sign (including an abnormal laboratory finding, for example), symptom, or disease temporally associated with the use of a medicinal product, whether or not considered related to the medicinal product. AEs may include the onset of new illness and the exacerbation of pre-existing conditions. Treatment-emergent AEs will be collected after signing the informed consent/assent through the last study visit. If there is a gap between the completion of the Study SD-005 and the start of Study SD-006, adverse events starting after the last study day or changing in severity or relationship to treatment within the gap will be recorded in the medical history for study SD-006. Continuing adverse events will be also captured in medical history for the extension study SD-006.

Medical review will take place to determine if any of AEs could be potentially related to the contamination of the study medication during the manufacturing process. The investigator's

verbatim term of both serious and non-serious AEs will be mapped to system organ class (SOC) and preferred terms (PTs) using the 19.1 version of the Medical Dictionary for Regulatory Activities (MedDRA). Partial dates will be imputed as the following:

1. If year is not missing and is after the year of first application of study drug:
 - a. If Month is missing, then Month will be imputed as January.
 - b. If Day is missing, then Day will be imputed as the first of the month.
2. If year is not missing and is the same as the year of the first application of study drug:
 - a. If Month is missing, then impute the Month as the month of the first application of study drug.
 - b. If Day is missing but Month is on or after the month of first application of study drug, then impute Day as the first day of - the month.
 - c. If the Day and Month are missing then impute Day and Month as the Day and Month of the first study drug application.
3. If year is missing then impute the year as the year of the first study drug application:
 - a. If Month is missing, then impute the Month as the Month of the first study drug application.
 - b. If Day is missing, then impute the Day as the day of the first study drug application.

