8.7.2. Adverse Events by Preferred Term and System Organ Class

For the first interim analysis serious AEs will be mapped to system organ class (SOC) and preferred terms (PTs) using the 19.1 version of MedDRA.

If there is a gap between the completion of the study SD-005 and the start of the study SD-006, adverse events starting after the last study day or changing the severity or relationship to treatment within the gap will be counted as medical history for the extension study SD-006. Continuing adverse events will also be captured in medical history for the extension study SD-006. If the severity or relationship to treatment changed on or after the first dose of study medication, then that AE is considered a TEAE after that change.

If an AE started after signing an informed consent/assent but before the first dose of study medication was taken in the study SD-006, then such an AE is non treatment-emergent.

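### An adverse event in the first-application month with a missing day is dated before first dose and can drop out of the treatment-emergent counts

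*SAP*

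**What the plan says.** Rule 3b of SAP 8.7.4.1 applies when the onset year is the year of first application and the day is missing: if the "Month is on or after the month of first application of study drug, then impute Day as the first day of the month". SAP 6.5.2 repeats it as rule 2b: "If Day is missing but Month is on or after the month of first application of study drug, then impute Day as the first day" (that is, the 1st).

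The neighbouring rules in 8.7.4.1 behave differently:

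- Rule 3c: "If the Day and Month are missing then impute Day and Month as the Day and Month of the first study drug application".
- Rule 5, for a completely missing start date where the event is ongoing or stopped after first application: "then impute the start date as the first date of study drug application".
- Rule 6 assumes treatment emergence only where the stop date falls before the start date.

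Two sections bear on classification. SAP 6.5.2 says: "Treatment-emergent AEs will be collected after signing the informed consent/assent through the last study visit". SAP 8.7.2 says that if an event began after consent but "before the first dose of study medication was taken in the study SD-006, then such an AE is non treatment-emergent". SAP 8.7.3 then provides: "Non treatment-emergent AEs, if any, will be listed". SAP 8.7.5 treats non treatment-emergent serious events the same way. Imputed dates are flagged in the listings.

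**The concern.** Rule 3b names the first-application month as within its scope and sets the 1st without comparing the result with the first-application date. The rules are therefore out of order. A record with less information (day and month missing, or no date for an ongoing event) gets an on-treatment date, while a record with more information (month known) gets a pre-treatment one. Rule 6 does not help, because an onset imputed too early does not put the stop date before the start date.

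Protocol 9.2 names adverse events as one of three ways the primary safety endpoint is assessed. Under the date-based rule in SAP 8.7.2, an affected event would be listed but not counted in the tables of treatment-emergent events, serious events or events leading to withdrawal. Under the SAP 6.5.2 wording it would be counted. Two programmers could produce different tables from the same data. Under either reading, the listing would show a wrong onset relative to first administration and an event duration too long by up to 30 days.

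**Working it through.** The plan states no figure on this point, so there is none to reproduce. The check applies rule 3b to every possible start date.

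**Inputs.** Rule 3b (SAP 8.7.4.1); the classification rule (SAP 8.7.2); exposures of 360 and 1440 days (SAP 5.1, before and after the second amendment). **Assumptions.** First-application dates and onset days are spread evenly over a 365-day year. For step 5 only, the missing-day rate is 1% to 10% and the event rate is constant over time.

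**1. Worked example.** First application is 18 March and true onset 25 March, recorded as March with day unknown. Rule 3b gives 1 March, 17 days before first dose. With the month missing as well, rule 3c would give 18 March, which is on treatment.

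**2. Start dates exposed.** All except the 1st of each month: (365 − 12)/365 = 353/365 = 96.7%.

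**3. On-treatment onset days moved before first dose.** In a month of L days, summing over start days, there are L(L + 1)/2 on-treatment onset days to month end. The L of these that belong to a start on the 1st are unaffected, which leaves L(L − 1)/2.

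- All: 7 × 496 + 4 × 465 + 406 = 5,738.
- Affected: 7 × 465 + 4 × 435 + 378 = 5,373.
- Share: 5,373/5,738 = 93.6%. Per patient: 5,373/365 = 14.72 days.

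Adding a leap year gives 10,774 of 11,505, again 93.6%.

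**4. Share of exposure.**

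- First 30 days: 5,373/(365 × 30) = 49.1%.
- 360 days: 14.72/360 = 4.1%.
- 1440 days: 14.72/1440 = 1.0%.

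**5. Share of all adverse events affected.** Multiply step 4 by the assumed missing-day rate:

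| Assumed missing-day rate | First 30 days | 360 days | 1440 days |
|---|---|---|---|
| 1% | 0.49% | 0.041% | 0.010% |
| 5% | 2.45% | 0.204% | 0.051% |
| 10% | 4.91% | 0.409% | 0.102% |

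**6. Does the imputed date also precede consent?** If consent is k days before first application, the 1st is strictly before consent when the start day is at least k + 2. The affected count per month is then (L − k)(L − k − 1)/2.

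| Assumed lag k (days) | Imputed before consent | Share of 5,373 |
|---|---|---|
| 0 | 5,373 | 100% |
| 1 | 5,020 | 93% |
| 3 | 4,350 | 81% |
| 7 | 3,154 | 59% |

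These events fall outside the literal wording of SAP 8.7.2, which requires onset after consent. The remainder (0%, 7%, 19% and 41%) are covered by it and become non treatment-emergent.

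**7. With a floor at first application.** Taking the later of the 1st and the first-application date, 0 of the 11,505 enumerated onsets precede first dose. Later months are unchanged.

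**The case against.** The strongest reply concerns the consequence, not the date. Consent and first dispensing are both scheduled at Visit 1. If application starts that day, the imputed 1st precedes consent as well, and no sentence in the SAP makes the event non treatment-emergent. Medical events before enrolment go to medical history, so an SD-006 adverse event record should be post-consent by construction, and SAP 6.5.2 would count it. **This stands in part.** In the same-day case the classification is undefined rather than stated wrongly, and loss from the counts is certain on the text only where consent preceded the imputed date. The imputed date is wrong in either case.

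The second reply is size. The 96.7%, 93.6% and 49.1% figures apply only once a day is missing. With 150 patients, 14.72 × 150 = 2,208 patient-days, or about 6.0 patient-years. At an assumed 2 to 10 events per patient-year and 1% to 10% missing days, that is about 0.1 to 6 events in the study. **This stands.**

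Third, there are partial safeguards. Imputed dates are flagged, all events are listed, and deaths, serious events and withdrawals have narratives. An event whose severity or relationship changes on or after first dose becomes treatment-emergent under SAP 8.7.2. Patients are counted once per preferred term, so a later occurrence preserves the patient count. **These limit the harm** but correct neither the date nor the event counts.

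Finally, the conflict between SAP 6.5.2 and 8.7.2 also exists for fully dated events, and 8.7.2 can be read as qualifying 6.5.2. That is fair. It still needs resolving here, because it decides what happens to these records.

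**Conclusion.** The concern holds. Rule 3b as written gives a pre-dose onset to on-treatment events in the first-application month whenever treatment did not start on the 1st, which contradicts the approach of rules 3c and 5. Whether such an event is then excluded depends on the gap between consent and first application and on which section the programmer follows.

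The number of events is likely to be small: 0.04% to 0.41% of events over 360 days, rising to 0.5% to 4.9% in the first 30 days. These ranges rest on an assumed 1% to 10% missing-day rate, evenly spread dates and a constant event rate; the documents supply none of these. The error is systematic, it can only remove early on-treatment events from the counts, and those counts serve the primary endpoint. It is a tabulation error, since the events remain visible in the listings. It should be fixed, but it does not threaten the study's conclusions.

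**What to change.** In SAP 6.5.2 (rule 2b) and 8.7.4.1 (rule 3b): where year and month equal those of first application and the day is missing, impute the date of first application, unless the stop date shows the event ended before it. Where the month is later, impute the 1st. Apply the stop-date exception before rule 6, which would otherwise blank the stop date and count the event as treatment-emergent. Rule 3a (2a in 6.5.2) needs the same floor, since a known day with a missing month can also fall before first application.

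State one definition of treatment-emergent that reconciles SAP 6.5.2 with 8.7.2, and say how an SD-006 event whose imputed onset precedes consent is classed.

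The cost is a short edit in each of two sections, one definition and one derivation in the adverse event dataset. The drawback is that some events that truly began earlier in that month, before first dose, would be counted. Treatment-emergent counts may rise slightly, which is the conservative direction for safety.
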